- To compare the effect of dual therapy versus monotherapy on plasma antioxidant capacity.
- To compare the effect of dual therapy versus monotherapy on inflammation biomarkers (VCAM-1 and adiponectin).
- To compare the effect of dual therapy of Dapagliflozin + Metformin versus Metformin monotherapy on cardio-metabolic risk factors (weight (kg), BMI (kg/m²), total cholesterol (mg/dL), HDL (mg/dL), LDLc (mg/dL), albuminuria (mg/24 hr), and blood pressure (mmHg)) in patients with T2D, after 12 weeks of treatment.

Methods

GENERAL DESIGN

STUDY DESIGN. Randomized, open-label, prospective, longitudinal phase IV clinical trial.

POPULATION. Adult men and women aged 18 to 77 years who meet the following Inclusion Criteria: Diagnosis of Type 2 Diabetes, with HbA1c 7.5% <12%, with BMI \geq 25 kg/m².

Exclusion Criteria: HbA1c >12%, T2D-related complications, HbA1c >9% with catabolic symptoms, creatinine clearance by CKD-EPI <60 ml/min/1.73m², Type 1 Diabetes or LADA, Concomitant clinically significant disease such as: liver, hematological, oncological, psychiatric or rheumatic disease, symptoms of severe glycemic dyscontrol such as marked polyuria or polydipsia + 10% weight loss within the last 3 months before enrollment, Known hypersensitivity to dapagliflozin or metformin or any of the drug excipients, Patients with bariatric surgery, Any major CV event / vascular disease within 3 months before signing consent at enrollment, pregnancy or lactation period, being hospitalized or having less than one month since hospital discharge for any cause.

SAMPLE SIZE. Using the difference of means formula and based on Henry et al., a reduction in glucose variability from 4.85 to 2.2 was estimated with an expected standard deviation of 2.8 in the MAGE index, with a statistical power of 80% and a confidence level of 95%. A total of 88 participants were obtained, 44 individuals in each treatment group. The CDC Epi InfoTM software was used. Patients will be randomized 1:1 to receive Dapagliflozin 10 mg/day + Metformin 2000 mg/day (n=44) or Metformin 2000 mg/day (n=44). GV will be measured with the iPro™ CGM system (Medtronic) at baseline and at the end of the 12 weeks of treatment.

VARIABLES. The primary dependent variable will be MAGE as a marker of GV. Other variables such as HbA1c, serum insulin, plasma antioxidant capacity, VCAM-1, and adiponectin will be analyzed. The independent variable will be the treatment group.

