Does the protocol involve the handling and labeling of biological samples? If applicable, mention the procedures that will be used

Yes, with the patient's initials, date of birth, internal laboratory patient number, and randomization number.

Information to ensure that obtained biological samples will not be used for permanent or immortal cell lines or purposes unrelated to the study

Qualified personnel will take samples for this activity and will be processed within the institution. Samples will not be sent to any other institution/company, so there is no risk of being used for purposes other than those stipulated in the protocol.

Description of treatment groups

Included subjects will be randomized 1:1 to receive:

- **Group 1:** Dapagliflozin 10 mg/day + Metformin 2000 mg/day and, if necessary, as mentioned previously, rescue treatment.
- **Group 2:** Metformin 2000 mg/day and, if necessary, as mentioned previously, rescue treatment. Treatments will be administered for 12 weeks. Patients who do not tolerate Metformin at a dose of 2000 mg will have their dose adjusted to 1500 mg daily. If patients do not tolerate 1500 mg daily, the dose will be titrated to 1000 mg daily. If they do not tolerate this dose, they will be withdrawn from the study.

Mechanisms for treatment assignment

The <https://www.google.com/search?q=randomization.com> tool will be used (The Table is attached as Appendix 1 of the protocol).

If a placebo group is used, include its justification

Not applicable

Criteria for premature withdrawal from the study

- Allergic reaction to any of the study medications or their excipients.
- Patients who do not tolerate Metformin 1000 mg/day.
- Severe life-threatening illness.
- Pregnancy during the study.
- Presence of acute renal failure (decrease in > 40% of glomerular filtration rate).
- Lactic acidosis or ketoacidosis.

Procedures for withdrawing a patient from the study

The patient will be notified of withdrawal from the protocol and will receive standard treatment, according to AACE 2019 guidelines (MET, GLP1 agonist, SGLT2 inhibitor, DPP4i, acarbose, thiazolidinediones, insulin, or sulfonylurea) and will be referred for follow-up at the secondary care level.

Criteria for premature (partial or complete) suspension of the study

NA

Selection Criteria

a) Inclusion criteria

- Subjects > 18-77 years old.
- Both men and women.
- HbA1c \geq 7.7% <12% (HbA1c from 9 to <12%: without catabolic symptoms).
- BMI $>$ 25 kg/m².

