A reduction in glucose variability from 4.85 to 2.2 was estimated with an expected standard deviation of 2.8 in the MAGE index, with an alpha value of 0.05 and a power of 0.80, resulting in a sample size of 88 subjects, with 44 subjects in each treatment group. No adjustments were included in the sample size calculation to estimate the number of subjects required for the

estimated differences in secondary variables.

Recruitment potential (number of subjects intended to recruit)

It is estimated that approximately 15% of the subjects who start the project and enter the pre-randomization period will not meet the criteria for the treatment period. Therefore, it is estimated that approximately 102 subjects will be assessed.

If multicenter, include the global and local sample number

Not applicable

Procedures for reporting deviations from the original statistical plan

A letter will be sent to the research committee for approval.

Possible discomforts resulting from the study

Frequency of follow-up visits, blood sample collection.

Potential risks

Those inherent to blood sampling.

Methods for detecting anticipated risks

Patients will be asked to report any side effects 24 hours a day. Patients will be able to contact the participating medical staff at any time.

Safety measures for timely diagnosis and prevention of risks

Patients reporting a side effect will be scheduled for evaluation.

Procedures to follow to resolve risks if they occur

Depending on the case, treatment for the complication or side effect will be provided, either with an outpatient prescription or the patient will be referred to the emergency department for assessment and treatment. Medical expense insurance will be available to cover treatment costs for patients associated with adverse effects secondary to the use of study medications.

Expected direct benefits

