## Statistical Analysis Plan

The sample size was determined using the mean difference formula:  $n = (Z\alpha / 2 + Z\beta) 2 * 2 * \sigma^2 / d^2$  a reduction in GV was estimated from 4.85 to 2.2 with an expected standard deviation of 2.8 in the MAGE index according to RR. Henry et al. [19] with an alpha value of 0.05 and a power of 0.80, resulting in a sample size of 88 subjects, with 44 subjects in each treatment group.

Patient recruitment began in October 2019 and was interrupted due to the SARS-COV-2 pandemic in March 2020. Nevertheless, patients who were already enrolled were followed up. Recruitment was normally restarted in March 2021; one of the inclusion criteria was adjusted, allowing HbA1c <13.0%, prior limit <12.0%. The last patient was recruited on December 6th, 2021. The complete study was concluded in March 2021.

A total of 88 patients met the selection criteria, signed the informed consent, and were randomized 1:1 on [www.randomization.com](http://www.randomization.com) (complete list of it is showed as supplementary material) to receive daily either DAPA 10 mg + MET 2000mg or MET 2000mg for 12 weeks. Both groups were monitored for GV using a CGM system for 7 days at baseline (W0) and on week 12 (W12).

Pre-randomization: patients were given 2000mg of MET daily for two weeks, only patients who tolerated this dose were included in the study and a treatment was randomly assigned.

Treatment: subjects who met the pre-randomization period and tolerated treatment were randomized 1:1 to receive either DAPA 10 mg/day + MET 2000 mg/day or MET 2000 mg/day for 12 weeks.

Of the total of 264 patients surveyed, a sample of 88 met the inclusion criteria and none of the exclusion criteria randomization DAPA+MET n=42 and MET n= 46. During the study, 7 patients discontinued (DAPA+MET n=1 and MET n=6). 80 patients concluded the study for 12 weeks (DAPA+MET n=41 and MET n=39). One patient was removed from the study (MET n=1) because he did not comply his medication intake nor the instructions during CGM. Study flowchart is displayed in Figure 1.

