The baseline characteristics were, the age [53.7  $\pm$  8.6 years DAPA+MET versus 50.9  $\pm$  11.8 years MET; p=0.2], TIR% Target: 70-180 mg/dL [55.5% (12.6-80.6) DAPA+MET versus 82.7% (26.1-95.1) MET; p=0.02], BMI [30.9  $\pm$  6.9 kg/m^2 DAPA+MET versus 30.1  $\pm$  3.2 MET; p=0.24], glucose [202.4  $\pm$  70.5 mg/dL DAPA+MET] versus 179.0  $\pm$  62.9 mg/dL MET; p=0.11], insulin [12.2  $\pm$  13.3  $\mu$ U/mL DAPA+MET versus 10.9  $\pm$  6.6  $\mu$ U/mL MET; p=0.57]. Complete baseline characteristics of the subjects included are summarized in Table 1.

All the measurements were carried out fasting. Student's T test was performed for normal variables to obtain significance. Skewed distribution variables are expressed with median and interquartile values of 25% and 75%, significance for these variables was obtained with the Mann Whitney U test.

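### The randomisation table is an appendix to the protocol of an open-label, single-site trial, and neither document describes any allocation concealment

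*Protocol*

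**What the plan says.** The protocol section *Mechanisms for treatment assignment* names a web randomisation tool and adds: "The Table is attached as Appendix 1 of the protocol". It says nothing else about how assignments are made. The preceding section, on treatment groups, gives the ratio: "Included subjects will be randomized 1:1 to receive" one of two regimens. The protocol's *Statistical Analysis* section says randomisation is stratified but gives no factors or block sizes.

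The design is stated as "Randomized, open-label, prospective, longitudinal phase IV clinical trial". One institution is listed as a site, and the form's item "If multicenter, include the global and local sample number" is answered as not applicable. The item on monitoring and auditing during the study is answered the same way.

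The SAP names the same web tool and says of the list: "complete list of it is showed as supplementary material". It reports the outcome as "randomization DAPA+MET n=42 and MET n= 46". It adds no step that separates the list from the people enrolling patients.

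**The concern.** Concealment means that whoever decides on a patient's entry cannot know the next assignment until that decision is fixed. It is distinct from blinding, and an open-label trial can and should have it. A table bound into the protocol, with no access rule, does not provide it: the protocol is the working document of the trial team, and the plan names no one who keeps the table from them.

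Foreknowledge could act where entry depends on judgement or timing. Some criteria leave that room: whether a concomitant disease is clinically significant, whether catabolic symptoms are present, whether a recent vascular event counts (explicitly left to the investigator), and whether metformin was tolerated in the run-in. If such calls followed the next assignment, the arms would differ in prognosis for reasons that adjustment for measured covariates cannot fully remove. The primary comparison of change in MAGE would then lose the protection of randomisation.

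**Working it through.** **1. Search for a safeguard.** Each element of concealment, against the two documents:

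| Element | Protocol | SAP |
|---|---|---|
| Source of the list | Web tool | Same web tool |
| Where the list is kept | Appendix 1 of the protocol | Shown as supplementary material |
| Who holds it | Not stated | Not stated |
| Envelopes, pharmacy or central release | Not mentioned | Not mentioned |
| Restricted access to Appendix 1 | Not mentioned | Not mentioned |
| Who enrols and who assigns | Not stated | Not stated |
| When an assignment is released | No randomisation row in the *Table of Times and Events* | After the two-week metformin run-in; not tied to the baseline CGM recording |

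The protocol states where the list is kept, and that place is one that the trial team can be expected to consult. This goes beyond a missing detail. The SAP list reads as retrospective reporting and is not itself a breach; the prospective appendix is the problem.

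**2. Is the 42/46 split informative?** The plan was 44/44; the SAP reports 42 + 46 = 88. Under unrestricted 1:1 randomisation:

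- P(split of 42/46 or more uneven) = 2 × P(X ≤ 42 | n = 88, p = 0.5) = 0.75.
- P(exactly 44/44) = 0.085.

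The split is unremarkable. If the list was instead built to give exactly 44/44, it needs an explanation, and only the list can supply it.

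**3. Are the baseline differences informative?** The SAP prints five baseline comparisons.

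- Time in range: "55.5% (12.6-80.6) DAPA+MET versus 82.7% (26.1-95.1) MET; p=0.02". If the five tests were independent, the chance of at least one p ≤ 0.02 is 1 − 0.98^5 = 0.096, about 10%. The SAP says the full baseline table (Table 1) holds the complete set.
- Fasting glucose: 202.4 − 179.0 = 23.4 mg/dL higher with DAPA+MET, printed p = 0.11. A t-test from the printed SDs (70.5 and 62.9) gives p = 0.104 with 42/46 and p = 0.122 with 41/39.
- Age, BMI and insulin: printed p = 0.2, 0.24 and 0.57.

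The denominators are not printed. Losses were 1 of 42 with DAPA+MET and 6 + 1 = 7 of 46 with MET, leaving 41 + 39 = 80. If the baseline figures describe completers, unequal attrition could contribute to the imbalance with no failure of concealment.

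**4. Does the planned analysis absorb an imbalance?** The *STATISTICAL ANALYSIS* paragraph under Methods compares changes by ANCOVA with age, sex, BMI, baseline HbA1c and time since diagnosis as covariates. Baseline HbA1c absorbs part of a glycaemic imbalance. Baseline MAGE, though measured in every patient by design, is not listed. Let δ be the between-arm difference in baseline MAGE left after those covariates, and β the slope of final on baseline MAGE. Change is final minus baseline, so the comparison of changes is shifted by (β − 1) × δ relative to one adjusted for baseline MAGE. The documents give neither β nor δ. For β between 0 and 1 the shift runs from the whole of δ to nothing, and it favours the arm with the higher baseline MAGE.

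**The case against.** The strongest reply is that the documents do not say who could open Appendix 1. A list may be appended for the ethics submission and left out of the copies that recruiting staff use. The appendix is not in the text available, nor is any statement of who enrolled and who assigned. This stands, and it limits the finding: a reader might infer that recruiters saw the next assignment, but the text supports only that no concealment is described and that the list is open to a holder of the full protocol.

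A reader might also infer from the 42/46 split and the difference in time in range that selection took place. Neither shows it, for the reasons worked above. Nor does it help to set the 23.4 mg/dL fasting difference against the 18.2 mg/dL effect quoted in the protocol's background: that figure is CGM mean glucose in patients already on metformin or insulin, and the baseline difference is not significant.

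It is also fair that much of eligibility is measured (HbA1c, BMI, renal function, pregnancy test) and that the schedule assesses entry criteria and metformin tolerance before week 0. This narrows the room for discretion without closing it. The SAP reports 264 patients surveyed and 88 randomised, so 176 were not; the available text does not give the reasons, and the flowchart is not shown.

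Sample labels carry the "internal laboratory patient number, and randomization number", which would let someone with the list identify a sample's arm. That concerns assessment rather than enrolment, and is minor in an open-label trial with a CGM-derived primary outcome and analyser or kit assays.

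Finally, the SAP reports recruitment as finished, so moving the list cannot change allocations already made. That shifts the remedy for these patients to disclosure, audit and analysis.

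**Conclusion.** The concern holds in a limited form. As written, the plan places the full list in the protocol of an open-label, single-site trial and describes no concealment, so selection bias cannot be excluded. The documents do not show that it occurred, and neither the split nor the baseline differences are evidence of it.

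The size of any bias cannot be derived. Saying that a person with the list can predict every assignment only restates the premise. The conclusion assumes that Appendix 1 travelled with the protocol and that no unwritten safeguard was in place. If one was, a short statement of it, confirmed by the enrolment record, would settle the point. If none was, readers need to know, because concealment is part of what justifies treating the arms as comparable at entry. The omission of baseline MAGE from the covariates is worth correcting in either case.

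**What to change.** **For any further enrolment.** Take the table out of the protocol. Have it held by someone who does not enrol patients, through the pharmacy or sealed envelopes, and release each assignment only once eligibility and the baseline CGM recording are documented. Add a randomisation row to the *Table of Times and Events*, and state the stratification factors and block sizes.

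**For the 88 already randomised.**

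- State who generated and held the list, who could see it, and when each assignment was released.
- Reconcile enrolment order and dates against the list. The SAP puts the last recruitment in December 2021 but the study's conclusion in March 2021, so correct those dates first.
- Explain 42/46 against the planned 44/44, and report any deviation from the list.
- State whether the baseline table covers randomised patients or completers.
- If concealment was absent, say so and limit the conclusion accordingly.

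**Analysis.** Add baseline MAGE as a covariate in the primary ANCOVA. Run one sensitivity model that also includes baseline time in range. Record both through the protocol's procedure for deviations from the statistical plan, and label them as added after recruitment.

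**Cost.** A short amendment, a small audit and one extra model; no more patients or visits. None of this can fully remove a selection bias if there was one.

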Glycemic variability (GV), which refers to daily glucose fluctuations, including preprandial, postprandial glycemia, and hypoglycemic episodes, could be associated with an increase in oxidative stress and the development of microvascular complications in Type 2 Diabetes (T2D). Although SGLT2 inhibitors have been shown to reduce GV, there is no evidence regarding their effect in newly diagnosed T2D patients when used at the initiation of pharmacological therapy, nor regarding their impact on oxidative stress.

Main objective: To evaluate the effect of dual therapy with Dapagliflozin + Metformin (DAPA/MET) versus Metformin monotherapy (MET) over 12 weeks on GV in patients with T2D.

Secondary objectives: To evaluate the effects on HbA1c, insulin, plasma antioxidant capacity, body composition, and cardiometabolic risk factors.

Hypothesis: The reduction in glycemic variability (measured using the mean amplitude of glycemic excursions, MAGE) will be greater in patients receiving dual therapy with Dapagliflozin + Metformin compared to those receiving Metformin monotherapy.

Methods: 88 patients with T2D without catabolic symptoms or complications, with HbA1c >7.5% and <12% and BMI >25 kg/m² will be included. Patients will be randomized 1:1 to receive Dapagliflozin 10 mg/day + Metformin 2000 mg/day (n=44) or Metformin 2000 mg/day (n=44). GV will be measured with the iPro™ CGM system (Medtronic) at baseline and the end of the 12 weeks of treatment.

Statistical analysis: The primary dependent variable will be MAGE as a marker of GV. Other variables such as HbA1c, serum insulin, plasma antioxidant capacity, VCAM-1, and adiponectin will be analyzed. Change deltas will be calculated for each group and compared using ANCOVA. A p-value ≤0.05 will be considered significant. All analyses will be performed with SPSS 20.0.

Background

There is growing evidence regarding the beneficial effects of sustained intensive glycemic control on the incidence and progression of complications in T1D and T2D [1]. HbA1c has been the main marker used to define glycemic control because it provides an average of glycemia in the 2 or 3 months before its measurement, with the American Diabetes Association recommending that HbA1c levels be maintained between 6.5% and <8%, depending on the individual characteristics of each patient [2]. Although HbA1c is a standardized, validated, and evidence-based marker, it is not useful for evaluating glycemic fluctuations over short periods [1].

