Definition of Follow-up Variables

- **Primary Variable:** Change from baseline in GV (MAGE) in mg/dL after 12 weeks of treatment between the DAPA+ MET group versus the MET monotherapy group.
- **Secondary Variables:**
 - Change from baseline (absolute difference) in HbA1c levels (%) after 12 weeks of treatment between the DAPA + MET group versus the MET monotherapy group.
 - Change from baseline (total difference) in insulin levels (μ U/mL) after 12 weeks of treatment between the DAPA + MET group versus the MET monotherapy group.
 - Change from baseline (absolute difference) in oxidative stress measurement (total antioxidant capacity) after 12 weeks of treatment between the DAPA + MET group versus the MET monotherapy group.
 - Change from baseline (total difference) in the measurement of inflammation biomarkers (VCAM-1 and adiponectin) after 12 weeks of treatment between the DAPA + MET group versus the MET monotherapy group.
 - Change from baseline (absolute difference) in body fat quantification after 12 weeks of treatment between the DAPA + MET group versus the MET monotherapy group.
 - Change from baseline (total difference) in the parameters of cardio-metabolic risk factors (weight (kg), total cholesterol (mg/dL), HDL (mg/dL), LDLc (mg/dL), albuminuria (mg/mg creatinine), and blood pressure (mmHg)) after 12 weeks of treatment between the DAPA + MET group versus the MET monotherapy group.

Methods for Data Collection

Electronic Record containing the clinical history collected via telemedicine (Phone call/Videocall, Whatsapp, Teams, Zoom or Google Forms), information gathered at each visit, notes containing patient physical examinations, physical activity questionnaires answered via telemedicine (Phone call/Videocall, Whatsapp, Teams, Zoom or Google Forms), Nutrition notes collected via telemedicine (Phone call/Videocall, Whatsapp, Teams or Zoom), and laboratory results. Patients will only be identified by their initials, date of birth, and the internal protocol folio number.

Monitoring and Auditing Procedures During Study Development

Not applicable

Criteria for Failure and Success

- **Failure:** No decrease in GV in the DAPA + MET group compared to the MET monotherapy group.
- **Success:** A decrease in GV in the DAPA+ MET group compared to the MET monotherapy group.

Sample Size

The sample size was determined using the difference of means formula:

$$n = (Z\alpha / 2 + Z\beta)^2 * 2 * \sigma^2 / d^2,$$

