A reduction in glucose variability from 4.85 to 2.2 was estimated with an expected standard deviation of 2.8 in the MAGE index (values based on the study by R. R. Henry et al., "Effects of Dapagliflozin on 24-Hour Glycemic Control in Patients with Type 2 Diabetes: A Randomized Controlled Trial," *Diabetes Technol. Ther.*, vol. 20, no. 11, pp. 715–724, Nov. 2018.), with an alpha value of 0.05 and a power of 0.80, resulting in a sample size of 88 subjects, with 44 subjects in each treatment group. No adjustments were included in the sample size calculation to estimate the subjects required for the estimated differences in secondary variables.

Description of techniques, devices, and/or instruments to be used (Including special mechanical, electronic, cybernetic equipment)

Continuous glucose monitoring will be performed using the iPro™2 Continuous glucose monitor, from Medtronic®, to determine the MAGE value as follows:

- **Calculation of Mean Amplitude of Glucose Excursion (MAGE):**
 - In the first step, all local maximum/minimum values are determined.
 - The next step is an evaluation of maximum/minimum pairs against the standard deviation (SD).
 - If the difference from minimum to maximum is greater than the SD, this variation from the mean measurement is retained.
 - If the local maximum/minimum is less than 1 SD, it is excluded from further calculations.
 - These channels are retained and summed to achieve the MAGE
- Glycated hemoglobin (HbA1c) will be measured using HPLC (Variant II Turbo, Biorad).
- Insulin levels will be measured with Access-2 equipment (Beckman Coulter, Inc.).
- Oxidative stress will be measured with the BioAssay Systems antioxidant assay kit (DTAC-

100) (QuantiChrom Antioxidant Assay Kit) (BioAssay Systems).

- VCAM-1 will be measured using ELISA kits (Merck Millipore, USA).
- Adiponectin measured using ELISA kits (Merck Millipore, USA).
- Body fat quantification by bioelectrical impedance with the Jawon scale, model⁵ IOI 353 - JMW160.
- Anthropometric variables will be measured using standardized techniques; these include height, weight, waist, and hip circumferences.
- BMI will be calculated using the equation: weight / height² (kg/m²).
- Blood pressure will be measured considering the mean of two determinations after sitting for at least 5 minutes.
- Mean arterial pressure (MAP) will be calculated with the formula: (systolic blood pressure * 0.33) + (diastolic blood pressure * 0.66).

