- Change from baseline (total difference) in the measurement of inflammation biomarkers (VCAM-1 and adiponectin) after 12 weeks of treatment between the DAPA + MET group versus the MET monotherapy group.
- Change from baseline (absolute difference) in body fat quantification after 12 weeks of treatment between the DAPA + MET group versus the MET monotherapy group.
- Change from baseline (total difference) in the parameters of cardio-metabolic risk factors (weight (kg), total cholesterol (mg/dL), HDL (mg/dL), LDLc (mg/dL), albuminuria (mg/mg creatinine), and blood pressure (mmHg)) after 12 weeks of treatment between the DAPA + MET group versus the MET monotherapy group.

Methods to be used to contact patients

Personal contact data such as landline and mobile phone numbers, email address will be obtained via Phone call/Videocall, Whatsapp, Teams, Zoom, or Google Forms. Due to the SARS-CoV-2 pandemic, investigators will conduct home visits and/or collect data and hold medical consultations via Phone call/Videocall, Whatsapp, Teams, Zoom, or Google Forms.

Statistical Analysis (Description of the information processing and presentation plan. Include justification for the statistical tests to be used)

Stratified randomization in both groups to balance patient types and control potential bias. The normality of variables will be analyzed using the Kolmogorov-Smirnov test. According to the distribution of variables, they will be expressed as mean and standard deviation (SD) or median and interquartile range (IQR) for normally or skewed distributed variables, respectively. GV will be determined using the MAGE index. Comparison between the two groups will be evaluated using ANCOVA. A p-value based on two-tailed tests ≤ 0.05 will be considered significant. All analyses will be performed with SPSS 20.0 (Chicago, IL). Patients experiencing an acute stress event during the study will be excluded from the analysis due to the impact on GV.

Justification of sample size (include study power and the p-value considered significant)

The sample size was determined using the difference of means formula:

$$n = (Z\alpha / 2 + Z\beta)^2 * 2 * \sigma^2 / d^2,$$

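### One p≤0.05 rule covers 12 or 13 secondary comparisons with no multiplicity control or exploratory label, so an isolated secondary result can be called significant even if MAGE shows nothing

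*Protocol*

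**What the plan says.** The significance rule appears three times in the protocol and is never tied to an endpoint. The Statistical Analysis section compares the groups by ANCOVA and states: "A p-value based on two-tailed tests ≤ 0.05 will be considered significant". The Summary lists MAGE and the other variables, says their changes will be compared by ANCOVA, and continues: "A p-value ≤0.05 will be considered significant". The statistical paragraph under Methods repeats the threshold.

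The comparisons under that rule are broad. Under Variables in Methods: "Other variables such as HbA1c, serum insulin, plasma antioxidant capacity, VCAM-1, and adiponectin will be analyzed". Definition of Follow-up Variables, repeated in section 39 (Outcomes and Variables), makes the secondary list formal. It contains HbA1c, insulin and antioxidant capacity, then "Change from baseline (total difference) in the measurement of inflammation biomarkers (VCAM-1 and adiponectin) after 12 weeks of treatment", then "Change from baseline (absolute difference) in body fat quantification after 12 weeks of treatment", and a cardio-metabolic group: "weight (kg), total cholesterol (mg/dL), HDL (mg/dL), LDLc (mg/dL), albuminuria (mg/mg creatinine), and blood pressure (mmHg". The Specific Objectives add BMI to that group: "cardio-metabolic risk factors (weight (kg), BMI (kg/m²), total cholesterol (mg/dL".

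On planning for these variables, the Sample Size section says: "No adjustments were included in the sample size calculation to estimate the subjects required for the estimated differences in secondary variables".

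The SAP restates the sample size, reports recruitment and baseline data, and names two-sample tests for normal and skewed variables. It gives no threshold, order or adjustment for secondary outcomes, so the protocol's rule stands.

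**The concern.** A plan with one primary variable and a dozen secondary ones usually says what a small secondary p-value will mean. This plan does say, and its answer is that it means significance. As written, an isolated p=0.04 on antioxidant capacity, VCAM-1 or adiponectin would be a significant finding whether or not MAGE differed between groups.

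That matters most for the markers with the least prior support. The Summary says there is no evidence on oxidative stress in newly diagnosed patients, and the Justification presents the answer as the start of a line of research. A chance result on one of these markers could therefore be reported as the first evidence of an effect.

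**Working it through.** The documents state no familywise error rate, so there is no plan figure to reproduce. The check has three steps.

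**1. Count the tests.** From Definition of Follow-up Variables:

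- HbA1c, insulin, antioxidant capacity: 3
- VCAM-1, adiponectin: 2
- body fat: 1
- weight, total cholesterol, HDL, LDLc, albuminuria, blood pressure: 6

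The total is 3 + 2 + 1 + 6 = 12, with blood pressure as one item. It is 13 if systolic and diastolic pressure are tested separately. The protocol does not say which, although its formula for mean arterial pressure uses both. BMI is not counted: it is defined as weight over height squared, so over 12 weeks in adults its change is essentially weight change rescaled for each person.

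**2. Ceiling: independent tests, every null true.** The chance of at least one p≤0.05 among k tests is 1 − 0.95^k.

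- k = 12: 1 − 0.95^12 = 0.460
- k = 13: 1 − 0.95^13 = 0.487

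The expected number of false positives is 0.05 × k, which is 0.60 or 0.65. Correlation does not change this expectation.

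**3. Relax both assumptions.**

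*Some nulls are false.* The Background reports that the drug class lowers HbA1c by 0.6 to 1%, modestly lowers blood pressure and reduces weight. It also cites a study of 16 patients in which dapagliflozin improved fat mass. A significant result on these would not be a false positive. Removing HbA1c, weight, body fat and blood pressure leaves 8 variables: insulin, antioxidant capacity, VCAM-1, adiponectin, total cholesterol, HDL, LDLc and albuminuria. Then 1 − 0.95^8 = 0.337, with 0.05 × 8 = 0.40 false positives expected. The Justification also mentions renal benefit in general terms. Treating albuminuria as affected too would leave 7, and 1 − 0.95^7 = 0.302.

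*The tests are correlated.* The documents give no correlations. The table uses normal test statistics with one common assumed correlation ρ; the values for ρ above 0 come from 400,000 simulated draws.

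| True nulls | ρ = 0 | ρ = 0.3 | ρ = 0.5 | ρ = 0.7 |
|---|---|---|---|---|
| 8 | 33.7% | 30.0% | 24.9% | 19.2% |
| 12 | 46.0% | 39.8% | 31.8% | 23.3% |
| 13 | 48.7% | 41.8% | 33.5% | 24.2% |

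For the three oxidative stress and inflammation markers alone, if independent and unaffected, 1 − 0.95^3 = 0.143.

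**The case against.** The strongest reply is that this trial has one primary variable, its hypothesis concerns MAGE only, and Criteria for Failure and Success rests on glycemic variability alone. If MAGE shows nothing, the trial has failed by its own criterion, and no secondary p-value can reverse that. This stands. A reader might infer that the trial's main conclusion carries an inflated error rate, but nothing in the documents supports that.

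The second reply is that the ceiling figures are a worst case. This also stands. LDL cholesterol is calculated from total cholesterol, HDL and triglycerides by the Friedewald equation, weight and body fat are clearly related, and the protocol itself expects real effects on several endpoints.

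Third, not sizing the trial for secondary variables concerns power. It does not raise the false-positive rate. That is correct. The sample-size statement is a reason to treat these variables as exploratory, but it does not cause the multiplicity problem.

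None of these replies supplies what is missing. Having a single primary variable protects the primary test. It does not tell a reader how to take a secondary result that the plan has already agreed to call significant.

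**Conclusion.** The gap is real and confined to secondary claims. The stated rule would label any of 12 secondary comparisons (13 with blood pressure split) significant at two-sided 0.05, without regard to the MAGE result or to the other comparisons.

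The risk of at least one false secondary claim is 46% to 49% at the ceiling. It is about 34% for 13 tests at ρ = 0.5, and about 25% to 34% with 8 true nulls as ρ goes from 0.5 to 0. Even the lowest cell in the table, 19%, is nearly four times the nominal 5%. These figures depend on the assumed common correlation and on which nulls are taken as true.

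A reader might infer that a false positive is about as likely as not. That needs independent tests and no drug effect on any secondary variable, and the protocol's own Background and its LDL formula argue against both. Adding BMI as a 14th independent test, which gives 51%, is not justified either.

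**What to change.** State in the SAP that the two-sided 0.05 rule applies to the MAGE comparison only. Report every secondary variable as a between-group difference in change with its 95% confidence interval, labelled exploratory, and make no significance claim for it. Say whether blood pressure is one variable or two.

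A fixed testing sequence or a Holm adjustment (first threshold 0.05/12 = 0.0042 for 12 tests) is an alternative only if it can be shown to have been fixed before any outcome results were seen. The SAP already reports 80 patients completing the 12 weeks, so an order written now may not count as prespecified. The documents also give no ranking of the secondary variables from which to derive one.

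The cost is one paragraph, plus the letter to the research committee that the protocol requires for changes to the statistical plan. No new data are needed and the primary analysis is unchanged. The downside is that no secondary endpoint can be called significant, including those, such as HbA1c, where an effect is expected.
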